Official Title: Building mental health resilience in the COVID-19 pandemic.

Brief Title: Brief Video Interventions for Depression

NCT Number: NCT04643964

Date of Document: 10/12/2020

IRB Request for Review of Human Subjects Research
Research protocol: Building mental health resilience in the COVID-19 pandemic.
PI: [name]

Objectives

The present study intends to examine the impact of cognitive-behavioral analog video interventions on depressive symptoms and coping skills. Our primary interest lies in comparing the efficacy of interventions focusing on one domain of coping skills to an intervention focusing on multiple domains of coping skills. We have tailored this intervention to address issues specific to the COVID-19 pandemic.

Background and Rationale

Cognitive-behavioral therapy (CBT) reliably reduces depressive symptoms (Strunk et al., 2017), but the causes of symptom change in CBT remain unclear (Cuijpers et al., 2019). Several studies have addressed this gap in understanding by examining the impact of CBT's individual components.

Teasdale and Fennell (1982) compared the effects of focusing on changing dysfunctional thoughts to focusing on gathering information on dysfunctional thoughts. They hypothesized that changing dysfunctional thoughts would predict greater depressive symptom reduction, compared to gathering information on dysfunctional thoughts. Five female treatment-resistant clients concurrently undergoing CBT participated in both procedures at different points in therapy. Belief in the identified thought and depressed mood were assessed before and after the procedures were conducted. Focusing on changing dysfunctional thoughts predicted greater depressive symptom change, compared to focusing on gathering information on dysfunctional thoughts.

Bruijniks et al. (2018) examined the impact of a cognitive skill acquisition procedure on depressive symptoms and coping skills. Seventy-two healthy undergraduate students were assigned to complete either a cognitive skill acquisition procedure or no procedure. On a following day, all participants completed a social stress test. Afterwards, participants completed measures of cognitive-behavioral therapy skill use, mood, dysfunctional thinking, and distress. Participants who completed the cognitive skill acquisition procedure showed higher cognitive therapy skill use but failed to differ from the control group on mood, dysfunctional thinking, and distress.

Bruijniks et al. (2020) continued their examination by assessing the impact of a cognitive skill acquisition procedure on CBT skill use and credibility of dysfunctional thoughts. Fifty-two female participants with depression were randomly assigned to one of two conditions: a cognitive skill acquisition procedure or a control procedure focusing on the theory of automatic thinking. Following the class, all participants were exposed to a sad mood induction, followed by a test of cognitive therapy skills. Participants who completed the cognitive skill acquisition procedure showed higher cognitive therapy skill use but failed to differ from the control group on credibility of dysfunctional thoughts and the strength of emotion associated with such thoughts.

The literature examining the impact of individual components of CBT on depressive symptoms is mixed. One reason for this discrepancy may be due to the potency of the skill

acquisition procedures. Even when completing a full course of treatment, many clients do not respond to CBT (Cuijpers et al., 2014). It is plausible that a single course focusing on CBT skills would fail to significantly impact depressive symptoms. As such, increasing the potency of such an intervention is essential. One way to strengthen skill acquisition procedures may be associated with the extent to which each coping skill is taught. Those who receive CBT are encouraged to act as their own therapist (Beck et al., 1979), which is pursued by practicing coping skills. As such, a one-time course focusing on a singular coping skill may be more beneficial than a similar procedure focusing on multiple coping skills.

We are interested in examining the effects of two types of video interventions aimed at teaching cognitive-behavioral coping skills. The first condition focuses on teaching one coping skill in depth (i.e., the “depth condition”). The second condition focuses on teaching several coping skills with less depth (i.e., the “breadth condition”). The third condition is a no-intervention control condition. We hypothesize the depth condition will predict greater changes in self-reported coping skills, a performance measure of coping skills, loneliness, and change in depressive symptoms, compared to the breadth condition. We hypothesize the depth and breadth condition will outperform the control condition on the same measures.

Procedures

A. Research Design

Participants will begin by reading a brief description of the study and will be directed to an online survey if interested in participating. Prior to informed consent, participants will be asked to fill out a pre-screening measure of depressive symptoms. The pre-screening measure is used only for eligibility purposes and will not be retained for data analysis. If a participant meets inclusion criteria, they will be prompted to read and review the informed consent document. Upon agreement, participants will fill out baseline measures. Then, participants will be randomly assigned to one of three conditions: (1) a brief intervention focused on one domain of coping skills (i.e., the “depth condition”) (2) a brief intervention focused on three domains of coping skills (i.e., the “breadth condition”) or (3) a no-intervention control condition. If participants are randomly assigned to the depth condition, they will be further randomized into one of three brief interventions: (1) a brief intervention focused on cognitive coping skills, (2) a brief intervention focused on behavioral coping skills, or (3) a brief intervention focused on interpersonal coping skills.

All participants will be administered measures assessing depressive symptoms, coping skills, problem-solving preferences, loneliness, demographics, and the impact the COVID-19 pandemic has had on participant’s lives. Participants in the intervention conditions will watch a series of videos describing coping strategies to deal with depressive symptoms. Following the videos, participants will be asked to fill out a measure assessing the perceived credibility of the brief intervention. Participants in the intervention conditions will be asked to practice the coping skills learned over the next seven days. Seven days after initial contact, all participants will be asked to fill out two measures assessing the quality of participant’s coping skills, a measure of depressive symptoms, and a measure of loneliness.

B. Sample

Utilizing Amazon's Mechanical Turk (MTurk) website, we will recruit approximately 501 participants who: (1) are 18 years of age or older, and (2) who score 10 or above on the Patient Health Questionnaire (PHQ-9). This cut-off was previously designated as being associated with moderate depression (Kroenke et al., 2001). Those employed on MTurk are paid to complete tasks offered online they voluntarily sign up for. Participation in this study will be restricted to those living in the United States. The study will be administered via Qualtrics. Participants will read an electronic copy of the consent form and will be required to indicate their consent to participate in the study. Participants will access the intervention and the follow-up portion of the study via an electronic device of their choosing.

C. Measurement / Instrumentation

Attention Questions. Attention questions are basic knowledge questions to assess the level of participant engagement. Three attention checks will be administered in the first portion of the study. Two attention checks will be administered in the second portion of the study.

Breadth/Depth Questionnaire (BDQ). The BDQ is a 10-item self-report scale measuring the extent to which participants prefer learning either single or multiple problem-solving strategies.

COVID-19 Pandemic Interference. This 6-item self-report questionnaire measures the extent to which the COVID-19 pandemic has interfered with participant's functioning, with responses ranging from "not at all" to "extremely". Item content was derived from the PROMIS Pain Interference item bank (Amtmann et al., 2010).

Demographics Questionnaire (DEM). The DEM consists of items regarding sex, age, ethnicity, education level, and income.

Credibility/Expectancy Questionnaire (CEQ). The CEQ (Devilly & Borkovec, 2000) is a 6-item self-report scale that measures the participant's perceived credibility of their current therapy. The questionnaire will be adapted to match the language of our brief intervention. The CEQ has demonstrated good internal consistency ($\alpha = .84-.85$).

Feedback Survey. The feedback survey is a 6-item self-report questionnaire that assesses the perceived quality of the video intervention.

Patient Health Questionnaire (PHQ-9). The PHQ-9 (Kroenke et al., 2001) is a 9-item self-report scale that measures depressive symptom severity. Internal consistency estimates for the PHQ-9 have been good ($\alpha = .84-.95$; Kroenke et al., 2010).

Quick Inventory of Depressive Symptoms-Self Report (QIDS-SR). The QIDS-SR (Rush et al., 2003) is a 16-item self-report scale that measures depressive symptom severity. Internal consistency estimates for the QIDS have been good ($\alpha = .86$; Rush et al., 2003).

Styles of Emotion Regulation Questionnaire (SERQ). The SERQ (Murphy et al., manuscript in preparation) is a 36-item self-report scale that measures the extent to which

respondents endorse four different domains of coping skills: cognitive, behavioral, interpersonal, and mindfulness.

UCLA Loneliness Scale, Version 3. The UCLA Loneliness Scale, Version 3 (Russell, 1996) is a 20-item self-report scale that measures subjective feelings of loneliness and isolation. Internal consistency estimates for the scale have been excellent ($\alpha = .89\text{-.94}$), along with good test-retest reliability over the course of a year ($r = .73$).

Ways of Responding Scale (WOR). The WOR (Barber & DeRubeis, 1992) is a performance measure intended to assess the quality of coping skills. Participants respond to six hypothetical stressful situations and are given initial thoughts regarding the stressful situation. Participants are asked to describe and rate the intensity of their mood, along with rating how vividly they imagine the stressful situation. Participants also rate how vividly they imagine having the initial thoughts provided, describe any further thoughts and presumed behaviors, and then re-rate the intensity of their mood. The WOR is rated by third party coders for the extent of coping skills endorsed. Intraclass correlation coefficients for WOR judgments have been good (ICC = .71; Strunk, DeRubeis, Chiu, & Alvarez, 2007).

Worksheets. In between watching videos, participants will be instructed to fill out relevant coping worksheets. These worksheets include: a thought record (Beck et al., 1979), a pleasure and accomplishment record (Beck et al., 1979) and a communication record, modeled on the DEAR skill used in DBT (Linehan, 1993). Participants will also be asked to fill out a relevant worksheet within the week between study participation.

D. Detailed study procedures

Access to the study will be provided via the MTurk website. After reading and reviewing a brief description of the study, those interested in participating will be directed to Qualtrics. Participants will be asked to fill out a pre-screening measure of depressive symptoms, which will take approximately 60 seconds to fill out. If a participant meets inclusion criteria, they will be presented the consent form. Upon agreement, participants will fill out baseline measures. Then, participants will be randomly assigned to one of three conditions: (1) a brief intervention focused on one domain of coping skills, (2) a brief intervention focused on three domains of coping skills, or (3) a no-intervention control condition. If participants are randomly assigned to the first condition, they will be further randomized into one of three brief interventions: (1) a focus on cognitive coping skills, (2) a focus on behavioral coping skills, or (3) a focus on interpersonal coping skills.

All participants will be administered measures assessing depressive symptoms, coping skills, problem-solving preferences, loneliness, and the impact the COVID-19 pandemic has had on participant's lives. All participants will be administered measures assessing depressive symptoms, coping skills, problem-solving preferences, loneliness, demographics, and the impact the COVID-19 pandemic has had on participant's lives. Filling out these measures will take approximately 30 minutes.

Each brief intervention consists of watching a series of videos. After each video, participants in the intervention conditions will be prompted to answer a series of questions to

practice the skills explained in the videos. Watching all videos and filling out all worksheets will take approximately 30 minutes.

Participants in the intervention conditions will then be asked to work on a coping skills worksheet over the next seven days. A coping skill worksheet will take approximately 10 minutes to fill out. Participants will receive an email seven days after participating in the brief intervention, asking them to take part in the following portion of the study. Before beginning the follow-up activity, participants in the intervention conditions will be asked to fill out an appropriate coping skills worksheet. An appropriate coping skills worksheet involves clear effort in filling out each of the components of the coping skill worksheet. Seven days after initial contact, all participants will be asked to fill out two measures assessing the quality of participant's coping skills, a measure of depressive symptoms, and a measure of loneliness.

Compensation

Incentives for those assigned to videos are \$0.75 for responding to the first portion of the study. If participants fill out an appropriate copy of a coping skill worksheet, they will receive an incentive of \$0.50. For responding to the second portion of the study, participants would receive \$1.25 as an incentive. The total incentive possible for participants assigned videos is \$2.50. Participants not assigned videos will receive \$0.50 as an incentive for responding to the first portion of the study. For responding to the second portion of the study, participants would receive \$1.00 as an incentive. The total incentive for both portions of the study would be \$1.50 for participants not assigned videos. As an incentive to participate, those who fill out the pre-screening measure will be eligible to win 1 of 2 \$50 Amazon gift cards. The odds of winning depend on the number of participants who fill out the pre-screening measure. If a participant begins but does not reach the last survey page the brief intervention or follow-up activity, they will not be compensated for that portion of the study. If a participant does not correctly answer any attention questions, they will not be compensated for that part of the study.

Minimization of risks

Data will be collected via Qualtrics. Once the data is obtained, it will be stored electronically on Qualtrics, Box, or University computers. Any identifiable information will be deleted after data collection and compensation is complete.

The proposed study poses minimal risk to participants. During the study, participants may experience mild discomfort from test instruments or videos. Participants will be allowed to withdraw from the study at any point and omit answers to any items for whatever reason. Any identifiable information will only be used to determine the proper amount of compensation. No identifiable information will be accessible in research published from this study. Participants have the option to not provide answers to any individual items during the study.

E. Internal Validity

To maximize internal validity in our study, we included conditions that involved coping skills in three domains and skills in each domain. With this form of design, we can be confident in attributing differences to either difference in time spent on a skill or the specific content with

the conditions. We also included attention checks to ensure participants maintain focus and that the study is not being filled out by automated systems.

F. Data Analysis

We will conduct a series of general linear models to examine if condition predicts differences in depressive symptoms, coping skills, and loneliness.

References

Barber, J. P., & DeRubeis, R. J. (1992). The ways of responding: A scale to assess coping skills taught in cognitive therapy. *Behavioral Assessment*, *14*, 93-115.

Beck, A. T., Rush, A. J., Shaw, B. F., & Emery, G. (1979). *Cognitive Therapy of Depression*. New York: Guilford.

Bruijniks, S. J. E., Los, S. A., & Huibers, M. J. H. (2020). Direct effects of cognitive therapy skill acquisition on cognitive therapy skill use, idiosyncratic dysfunctional beliefs and emotions in distressed individuals: An experimental study. *Journal of Behavior Therapy and Experimental Psychiatry*, *67*, 101460. <https://doi.org/10.1016/j.jbtep.2019.02.005>

Bruijniks, S. J. E., Sijbrandij, M., Schlinkert, C., & Huibers, M. J. H. (2018). Isolating therapeutic procedures to investigate mechanisms of change in cognitive behavioral therapy for depression. *Journal of Experimental Psychopathology*, *9*, 1-11. <https://doi.org/10.1177/2043808718800893>

Official Title: Building mental health resilience in the COVID-19 pandemic.

Brief Title: Brief Video Interventions for Depression

NCT Number: NCT04643964

Date of Document: 8/30/2022

Statistical Analysis Plan

Data were analyzed using SAS 9.4. Participants who failed one or more attention checks (e.g., “What is $124 + 1$?”) were excluded from analyses. We tested for possible condition differences between the entrée (i.e., an intervention focused on teaching participants one coping skill), sampler (i.e., an intervention providing an introduction to three coping skills), and no-intervention control conditions in depressive symptoms, coping skills, loneliness, age, and gender. We also evaluated whether there were condition differences in credibility or expectancy following the intervention.

To test the primary hypotheses, we evaluated potential condition differences in each outcome variable (viz., depressive symptoms, coping skills frequency, coping skill quality, and loneliness) at Time 2, controlling for the Time 1 level of that same variable. Baseline depressive symptoms were also included as a covariate in all models. Other covariates considered in these models were age, gender, and COVID interference. Covariates that were significant at $p < .05$ were included in primary models. The only significant covariate identified was gender, which was limited to models examining coping skill frequency. The entrée condition’s three separate interventions (cognitive skills, behavioral skills, or interpersonal skills) were combined for these analyses. In analyses of the coping skill frequency scale (the SERQ), repeated-measures regression with an unstructured covariance matrix was used to model the three subscales of interest (Cognitive, Behavioral, and Interpersonal) as repeated measures reflecting CBT skills. A variable indicating which skill was targeted in the assigned intervention was also included in the model. For instance, participants in the behavioral entrée had a score of ‘1’ for the line reflecting the behavioral subscale and a ‘0’ for the cognitive and interpersonal subscales. Participants in the sampler condition had scores of ‘1’ for all three subscales.

In exploratory analyses, we conducted other specific comparisons of interest. These analyses included: comparing the entrée and sampler conditions without including the control condition and comparing each of the entrée variations with each other. We examined condition differences in risk of dropout using logistic regression. We also used logistic regression to examine condition differences in completing coping skill worksheets. Finally, we evaluated two potential moderators of any entrée versus sampler difference in outcomes: initial depression severity and preference for using one vs. multiple skills. We did not correct for multiple comparisons.

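### Does admitting age, gender and COVID interference to the primary models only when p < .05 in the trial's own data call for a different covariate plan?

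*SAP*

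**What the plan says.** The SAP models each of four Time 2 outcomes (depressive symptoms, coping skill frequency, coping skill quality, loneliness) "controlling for the Time 1 level of that same variable". It adds that "Baseline depressive symptoms were also included as a covariate in all models". For the depressive-symptoms outcome these two terms appear to be the same variable, so that model probably has one fixed covariate and the others two.

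The SAP then turns to optional terms: "Other covariates considered in these models were age, gender, and COVID interference". The rule is "Covariates that were significant at $p < .05$ were included in primary models", and its result is stated: "The only significant covariate identified was gender, which was limited to models examining coping skill frequency". So the SERQ (coping skill frequency) models carry gender, the other three outcomes carry only the fixed covariates, and no model carries age or COVID interference.

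The protocol's section F, Data Analysis, says only "We will conduct a series of general linear models to examine if condition predicts differences" in the outcomes. It gives no covariates and no selection rule. The SAP is dated 8/30/2022, is written in the past tense, and already contains the outcome of the screen.

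**The concern.** Choosing adjustment variables by a significance threshold in the data under analysis is usually discouraged. A covariate is useful because it is prognostic, and a p-value cut detects that unreliably. The same variable can enter one model and miss another by chance, which makes the outcomes look as if they were treated differently for a reason.

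Here the models concerned test the primary hypotheses. Nothing shows that the candidate list or threshold was fixed before the data were seen, and the SAP does not say whether candidates were tested together or singly. If the screen left room for choice, an analyst could in principle settle on the adjustment that gave the preferred condition effect. The natural remedy would be one common covariate set for all four outcomes, whatever the p-values.

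**Working it through.** **Inputs.** From the SAP: 3 candidates, 4 outcomes, threshold .05, gender selected for SERQ only. From the protocol's section B: "we will recruit approximately 501 participants who" meet the entry criteria. The analysed N and the allocation ratio are not given, so equal arms and N between 249 and 501 are assumed. The plan states no figure of its own to reproduce.

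**1. How erratic is the screen?** There are 3 × 4 = 12 tests.

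- If no candidate is prognostic, 12 × 0.05 = 0.6 false entries are expected. The chance of at least one is 1 − 0.95^12 = 0.46 if the tests are independent, falling to 0.26 at a between-outcome correlation of 0.9.
- If gender had a partial correlation of 0.10 with every outcome, its chance of entering a given model is about Φ(atanh(0.10) × √(N − 7) − 1.96): 0.61, 0.51 and 0.40 at N = 501, 400 and 300. Two outcomes would then be treated differently with probability 2p(1 − p), which is 0.48, 0.50 and 0.48 (independence assumed).

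So gender passing for one outcome is weak evidence that it matters only there. That part of the concern is right.

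**2. Does this affect the condition test?** Baseline measures precede randomisation, and the protocol's seven-day follow-up list does not include the three candidates. Apart from chance imbalance they are therefore unrelated to condition. Including or omitting them leaves the condition estimate centred on the same value, and the screen looks at the covariate's p-value, not at condition's.

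Type I error of the two-degree-of-freedom condition test was simulated with no true effect (ANCOVA, three equal arms, 10,000 runs per row, Monte Carlo standard error about 0.2 points):

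| N | Coefficient of each candidate | Fixed covariates only | All three always in | Screen, condition in screening model | Screen, condition left out |
|---|---|---|---|---|---|
| 501 | 0 | 5.42% | 5.24% | 5.41% | 5.38% |
| 501 | 0.1 | 5.01% | 4.88% | 5.04% | 4.93% |
| 501 | 0.2 | 5.55% | 5.17% | 5.17% | 5.17% |
| 300 | 0 | 4.99% | 4.84% | 5.05% | 4.99% |
| 300 | 0.1 | 5.13% | 4.88% | 5.12% | 4.96% |
| 300 | 0.2 | 5.24% | 5.07% | 5.07% | 5.07% |

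The SERQ model was simulated separately: three subscales, unstructured covariance, targeted-skill indicator, candidate coefficients 0, 0.07 or 0.15, N = 249, 351 or 501, 4,000 runs per setting. Type I error for entrée versus sampler was 4.6–5.9% with the screen and 4.5–5.9% with all three, never more than 0.2 points apart in the same setting. Mean standard errors agreed to about 0.2%, and the estimate moved by an SD of at most 0.09 SE.

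**3. How far can an estimate move?** With condition and covariate independent, adding a covariate of unit SD shifts the condition estimate by an SD of about β/σ standard errors, where β is its coefficient and σ the residual SD. Several covariates combine in quadrature. With an assumed residual variance of 0.384 for the three-subscale mean, σ = √0.384 = 0.62.

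- Three covariates at 0.15: √3 × 0.15/0.62 = 0.42 SE (simulated 0.42–0.43).
- Gender alone at 0.15: 0.15/0.62 = 0.24 SE (simulated about 0.25).
- Gender alone at 0.07: 0.07/0.62 = 0.11 SE (simulated 0.12–0.13).

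The first line does not describe this trial: with three covariates that strong, gender alone is selected in at most 0.15% of simulated trials.

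For a candidate that fails the screen, |t| < 1.96. Since β/σ is about t/√N, its omission shifts the estimate by an SD below 1.96/√501 = 0.09 SE, or 1.96/√249 = 0.12 SE at the smallest N assumed.

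**4. What would a common set alter?** The SERQ model would keep gender. Each of the other changes adds terms that failed the screen, with the small shifts just shown. There is also a cost. The protocol lets participants "withdraw from the study at any point and omit answers to any items for whatever reason", so without an imputation rule complete-case loss over three covariates is 1 − (1 − m)^3: 3%, 6% or 14% at assumed omission of 1%, 2% or 5% per covariate.

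**The case for a change.** The strongest case for a change is about discretion, not error rates. The simulations assume that the rule was applied mechanically, and the documents cannot show that it was. With gender alone moderately prognostic, the SERQ estimate with and without it differs by an SD of about 0.25 SE, enough to tip a borderline p-value. On this view, one set used regardless of significance would close the question for a few lines of text.

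Part of this stands. The timing of the rule and the way candidates were tested are undocumented, and a reader would be helped by knowing them and by seeing the SERQ result without gender.

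The rest does not carry. The SAP discloses the candidates, the threshold, the result and the one model affected. For three outcomes the screen added nothing, so their primary models already are the fixed-covariate models and leave no choice to suspect. If gender truly predicts SERQ scores, the gender-adjusted model is the more precise one, and the common set would contain gender as well. Finally, the data have been analysed. A set chosen now is another choice made afterwards and cannot restore prespecification.

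**Conclusion.** No change to the plan. The screen is not how one would ideally choose covariates, and it can make adjustment differ between outcomes by chance. Followed as written, though, it gives sound tests. Type I error stays within about 0.2 points of a model containing all three candidates, standard errors are practically equal, and estimates differ from that model by an SD of roughly 0.1 SE or less. A further simulation found that the significance verdict changed in at most about 1% of trials.

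These figures assume equal arms, an analysed N between 249 and 501, candidates measured before the intervention, and mechanical use of the rule. Only the last cannot be checked from the documents, and its reach is limited to one covariate in one of four outcomes. A sentence in the trial report on when and how the screen was run would settle it.

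### The SERQ model adjusts for a targeted-skill variable fixed by arm and subscale, so its condition terms are not all the randomised condition differences unless taught and untaught skills change equally

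*SAP*

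**What the plan says.** The SAP (dated 8/30/2022, written in the past tense) describes the test of the primary hypotheses as follows: "we evaluated potential condition differences in each outcome variable", measured at Time 2 and adjusted for Time 1. SERQ coping skill frequency is one of four such outcomes. The three entrée versions are pooled into one condition.

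For the SERQ only, "repeated-measures regression with an unstructured covariance matrix was used to model the three subscales of interest", and one more term enters: "A variable indicating which skill was targeted in the assigned intervention was also included in the model". An entrée participant scores 1 on the row for the taught subscale and 0 on the other two. "Participants in the sampler condition had scores of" 1 on all three rows. The SAP gives no coding for control. It does not say whether the variable interacts with condition, or which coefficient or contrast is the test.

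The Protocol uses the names depth (entrée) and breadth (sampler). Its Objectives section says: "Our primary interest lies in comparing the efficacy of interventions focusing on one domain of coping skills" against an intervention that covers several. Background and Rationale gives two hypotheses: "We hypothesize the depth condition will predict greater changes in self-reported coping skills" (among other outcomes) relative to breadth, and "We hypothesize the depth and breadth condition will outperform the control condition on the same measures".

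**The concern.** The targeted-skill variable is not a baseline covariate. It is determined by the randomised assignment and the subscale, so it can absorb part of the intervention effect. Within a participant it varies only in the entrée arm, so its coefficient is learned there. An additive model then carries that coefficient over to the sampler arm, and to control according to a coding that is not given.

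The condition terms may therefore answer a different question from the one in the hypotheses. A null or a positive SERQ result could be read as a statement about coping skills in general when another quantity was tested. The other three outcomes do not use this variable and are not affected.

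**Working it through.** The documents give no SERQ effect, SD, correlation or power figure, so there is no stated result to reproduce. The check is algebra on the coding, followed by an illustration.

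**Inputs from the SAP.** The mean of the variable T over the three subscales is 1/3 in the entrée arm and 1 in the sampler arm. For control it is not stated; call it c.

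**Model assumed.** An additive model, E[Y] = a_k + bE·entrée + bS·sampler + g·T, with subscale intercepts a_k. Let dT and dU be the entrée effects against control on a taught and an untaught skill, s the sampler effect, and g = dT − dU.

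**Algebra.** Matching cell means gives bS + g = s + cg and bE = dU + cg.

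| Comparison | Term in the model | Arm difference averaged over subscales | Equal when |
|---|---|---|---|
| Sampler − control | s − (1−c)g | s | c = 1 or g = 0 |
| Entrée − control | dU + cg | dU + g/3 | c = 1/3 or g = 0 |
| Entrée − sampler | dT − s | dU + g/3 − s | g = 0 |

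The last row differs by dT − dU − g/3 = 2g/3 whatever c is. With c = 0, the sampler-control term is s − g, a sampler effect on an untaught skill. The design has no such cell.

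**Illustration (all values assumed).** 167 per arm (about 501/3; the Protocol's Sample section gives about 501 and no allocation ratio), residual SD 1, subscale correlation 0.5, s = 0.25.

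| | Sampler − control | Entrée − control | Entrée − sampler |
|---|---|---|---|
| g = +0.10 (dT 0.30, dU 0.20): average | 0.250 | 0.233 | −0.017 |
| term, control coded 0 | 0.150 | 0.200 | +0.050 |
| term, control coded 1 | 0.250 | 0.300 | +0.050 |
| g = −0.10 (dT 0.20, dU 0.30): average | 0.250 | 0.267 | +0.017 |
| term, control coded 0 | 0.350 | 0.300 | −0.050 |
| term, control coded 1 | 0.250 | 0.200 | −0.050 |

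**Precision.** The variance of one participant's three-subscale mean is (1 + 2×0.5)/3 = 0.667, so the SE of an averaged difference is √(2×0.667/167) = 0.089. The SE of g is √(0.5/(167×2/3)) = 0.067. With control coded 0, the sampler-control SE is √(0.089² + 0.067²) = 0.112. It is 0.113 versus 0.080 at correlation 0.3, and 0.111 versus 0.098 at 0.7. With control coded 1, the entrée-control SE is 0.100 versus 0.089. So at g = 0 there is no bias, only lost precision.

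**Rejection rates.** If the sampler has no effect (s = 0), g = ±0.10 and control is coded 0, the sampler-control term is ∓0.10. The rejection rate is Φ(−1.96 + 0.10/0.112) + Φ(−1.96 − 0.10/0.112), about 15% instead of 5%. Under the global null it stays at 5%. A two-degree-of-freedom condition test also changes. Its power at g = +0.10 / 0 / −0.10 is 48/73/91% with control coded 0 and 87/81/75% with control coded 1, against 81/83/86% for the equal-weight averages.

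**Simulation** (600 trials per scenario, estimated unstructured covariance, baseline covariate). The mean sampler-control estimate from control 0 / control 1 / averages was 0.150/0.253/0.253 at g = +0.10 and 0.356/0.252/0.252 at g = −0.10. With s = 0, control coded 0 rejected in 16–17% of trials, against 4–7% for the averages.

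**Is dropping T enough?** No. Unstructured-covariance weighting of unequal subscale effects need not return the plain average. With assumed SDs 0.8/1/1.2, correlations 0.7/0.3/0.4, sampler effects 0.40/0.25/0.10 (mean 0.25), dT 0.30, dU 0.20 and entrée versions of 70/55/42, the additive model without T gives sampler-control 0.326 and entrée-control 0.238. Condition-by-subscale averages give 0.250 and 0.233, which are the targets.

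**The case against.** The strongest reply is that a taught-skill contrast was intended and is sensible. The Protocol's rationale turns on "the extent to which each coping skill is taught", and its Internal Validity section attributes differences partly to time spent on a skill. Two-thirds of an equal-weight entrée average comes from skills that were not taught. The entrée-sampler term, dT − s, compares a taught skill in both arms and keeps the protection of randomisation. The Protocol does not say that self-reported coping skills means an equally weighted average of subscales.

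This stands in part. The entrée-sampler term is coherent, and the equal-weight average is a reasonable reading of the hypothesis, not one the documents declare. But the SAP does not declare the taught-skill reading either, and that reading does not settle the control comparisons. They are taught-skill effects only if control is coded 1, whereas 0 is the natural code for participants who were taught nothing.

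Three further points are fair. The SAP does not say the model is additive, and the reported contrasts may have added g back. With control coded 0 and g > 0, both control comparisons are pulled down, so a spurious sampler benefit would need g < 0. And every magnitude above is illustrative; 167 per arm also ignores attention-check exclusions and dropout. These points limit what can be said about size and direction, but they do not remove the mismatch in the model as described.

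**Conclusion.** The concern holds and should be fixed. On the ordinary additive reading, the SERQ condition terms cannot all equal the randomised differences averaged over subscales unless g = 0, whichever control coding was used. The discrepancies are (1−c)g for sampler-control, (c − 1/3)g in absolute size for entrée-control, and 2g/3 for entrée-sampler. At an assumed g of ±0.10 SD this is enough to reverse the sign of the entrée-sampler comparison in the example.

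Confidence is high that the variable is fixed by arm and subscale, and high in the algebra under additivity. The size and sign of g in this trial are unknown, and so is whether the reported contrasts corrected for it. The reach is one of four outcomes.

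**What to change.** 1. State in the SAP the control coding of the targeted-skill variable, whether it interacts with condition, and the exact contrast tested for each SERQ hypothesis.
2. For the SERQ condition hypotheses, fit the repeated-measures model without the targeted-skill variable and with condition-by-subscale terms. Report the equal-weight average of the three subscale differences for sampler-control, entrée-control and entrée-sampler. Analysing the mean of the three subscales is an alternative.
3. Keep the targeted-skill model as a separately named analysis of the effect on a taught skill.
4. Because the SAP is retrospective, label the addition a post hoc reanalysis and show it beside the existing result, not in place of it.

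The cost is one added MODEL statement and one ESTIMATE statement on data already collected, plus SAP wording. The drawbacks are the post hoc label and, when subscale variances differ, a slightly larger SE than an additive model without the variable (0.087 versus 0.082 in the unequal-variance example).
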